1 7. Neuropsychological testing: to provide measures of immediate and delayed
2 memory, conceptualization, copying, perceptual discrimination, and language.
3 Each of these tests will be administered at baseline, 90 days and 180 days except
4 the MMPI that will be administered at baseline and 180 days only.

5 a) Rey Auditory - Verbal Learning Test (RAVLT)

6 Rationale: it is similar to those tests (i.e., California Verbal Learning Test¹⁹,
7 and Selective Reminding Test) shown sensitive to Lyme-related memory
8 loss and it has several alternate forms. (time = 20 minutes)
9

10 b) Symbol-Digit Modalities Test A test that requires attention and
11 concentration in addition to visual perception.

12 Rationale: shown to be sensitive by Halperin²⁰ to Lyme-related decline
13 performance. (time = 2-3 minutes)
14

15 c) MMPI A personality inventory and psychopathology screen.

16 Rationale: previously used to compare Lyme and fibromyalgia patients by
17 Kaplan²¹ and may reveal differences in personality profile of chronic
18 Lyme patient.^{22 23}(time = 45 minutes)
19

20 d) Beck Depression Inventory A depression index.

21 Rationale: previously used in several Lyme studies to assess depression and
22 compare depression to other patient groups. (time = 5-10 minutes)
23

24 e) California Computerized Assessment Package (CalCAP) A series of
25 continuous performance reaction time tests with large normative sample.

26 Rationale: this is a more sensitive test of attention and concentration than
27 tests previously used. (time = 10-15 minutes)
28

1 f) Controlled Oral Word Association (COWA) A word generation test.
2 Rationale: Krupp ²⁴ showed differences on this test between controls and
3 previously treated Lyme patients and it has several alternate forms. (time =
4 5 minutes)

5
6 g) Benton Visual Retention Test (BVRT)
7 Rationale: Halperin and Kaplan showed Lyme effects using this or a similar
8 test (Wecksler) of memory. There are 3 alternate forms of the BVRT
9 and only two of the Wecksler. (time = 15 minutes)

10
11 All test scores will be transformed into standard scores that will be calculated from
12 published, age-corrected normative data. According to a previously described
13 system, evidence of memory impairment is defined as scores that are 2 SD below
14 the normative mean on any one of the tests of memory or more than 1 SD below
15 the mean on two of the tests. A score of 70 or above on the Minnesota Multiphasic

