25 measure physical functioning, role-physical, bodily pain, general health, vitality, social
26 functioning, role-emotional and mental health. The eight multi-item scales are
27 hypothesized to form two distinct higher-order factors, physical and mental, which
28 provides the basis for scoring the SF-36 physical and mental health summary scales.
29 Three additional multi-item scales from the medical outcomes study (MOS) will be used
30 to measure cognitive functioning, pain, and role functioning but they will not be used for

1 the primary analysis of efficacy of antibiotic treatment. The SF-36 Health Survey (and
2 the additional MOS measures) will be administered to study participants four times: at
3 baseline, at one month (end of parenteral treatment), at three months (end of treatment),
4 at six months and at one year..

5
6 To document the burden of Lyme disease on health-related quality of life, baseline scores
7 for the SF-36 (and MOS scales) will be compared to general population norms. General
8 population norms will be age adjusted to correct for differences in age between the study
9 sample and the general population. Norm-based comparisons of SF-36 (and MOS scale
10 scores) will also be conducted with 1, 3- and 6- month follow-up scores in both treated
11 and placebo groups to evaluate change in the study participant HQL profile relative to
12 general population norms.

13
14 To assess changes in HQL over time for study participants, a change score for each SF-36
15 (and MOS scale) will be calculated by subtracting the baseline score from the 1 month
16 score, the 3 month score and the 6 month score. Using two standard errors of
17 measurement (SEM), individual patients will be classified into 3 change categories: (1)
18 those whose follow-up scores did not change more than would be expected by chance
19 (“same group”); 2) those whose follow-up scores improved (more than 2 SEM's) more
20 than would be expected by chance (“better group”); and 3) those whose follow-up scores
21 declined (more than 2 SEM's) more than would be expected by chance (“worse group”).
22 Based on prior studies with the SF-36, a 2 SEM change is 6.5 points for the SF-36
23 physical health summary scale and 7.9 points for the SF-36 mental health summary scale.

24
25 An overall determination of change in health status will be determined for each patient
26 from the results of the two SF-36 summary scales (and the three MOS scales). Patients

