27 will be scored as improved if they are better on both scales or better on one scale and are
28 not worse on the other scale.

1 The primary analysis will be an intent-to-treat analysis of all patients enrolled in the
2 study. For secondary analysis, patients will be evaluated who have received at least 75%
3 of the course of study therapy. Both analyses will involve comparisons between the
4 proportion of patients improved at 6 months in the placebo and treated groups. A
5 secondary analysis will compare the groups at the end of parenteral (30 days) and total
6 active treatment (90 days). Comparison will consist of a χ^2 test at a significance level of
7 0.05, together with an estimate of treatment efficacy (risk ratio and risk difference) with
8 95% confidence intervals. As secondary and exploratory analyses, we will check to see if
9 efficacy differs across subgroups by examining interaction terms in a multivariate
10 analysis. We will also determine whether changes in patient performance on the
11 supplementary MOS scales correlate with changes in the SF-36. Such subgroup analyses
12 will need further confirmation in future studies. Nevertheless, their discovery may
13 suggest important treatment interactions.

14
15 Tests will be done to ensure that no important potential confounders are unevenly
16 distributed between patient groups. Regression analysis will be performed to determine
17 the effect on results if any confounders are identified. An analysis stratified by duration
18 of symptoms of chronic Lyme disease will be performed. An analysis stratified by site
19 also will be performed to ensure that the results are not dependent on site. Among
20 potential confounders and interaction variables are demographic variables (e.g., age, sex,
21 race, education and location), medical history variables (e.g., previous psychiatric illness,
22 prior history of arthralgia or arthritis, duration of symptoms, and interval between onset
23 of acute Lyme disease and chronic symptoms) and physical examination variables (e.g.,
24 tender points and findings on neurologic examination).

25 26 C. Statistical Analysis

27 28 Study Sample Size

1 For a long course of high dose antibiotics to show efficacy there should be a substantial,
2 durable difference between the antibiotic treated and the placebo groups. We shall
3 assume that the natural healing rate is 0.40 or 40%. For an efficacy study in which the

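### The baseline comparison of SF-36 and MOS scores with population norms adjusts for age only, so any difference in sex mix stays in the estimated burden; the effect is small and cheap to remove

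*Protocol*

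**What the plan says.** Section VIII.B (Evaluation of Antibiotic Therapy Efficacy) plans a comparison with an external population: "To document the burden of Lyme disease on health-related quality of life, baseline scores" on the SF-36 and MOS scales are set against general population norms. It then fixes the correction: "population norms will be age adjusted to correct for differences in age between the study" sample and the general population. No other adjustment of the norms is named. The comparison is repeated after baseline: "scores) will also be conducted with 1, 3- and 6- month follow-up scores in both treated" and placebo groups, to follow the participants' profile relative to the norms.

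Later in VIII.B, sex and education appear in a list: "potential confounders and interaction variables are demographic variables (e.g., age, sex", followed by race, education and location. That paragraph is about imbalance between the randomised groups.

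Section VI.A, item 7, uses norms separately for the neuropsychological tests. Scores are standardised from "published, age-corrected normative data", and "evidence of memory impairment is defined as scores that are 2 SD below" "the normative mean on any one of the tests of memory or more than 1 SD below" the mean on two of them.

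**The concern.** The protocol adjusts the norms for age because the sample may not have the same age distribution as the general population. The same reasoning applies to sex whenever scores differ between the sexes. Randomisation gives no protection here, because the comparator is an outside population and not the other arm. Nor does the bias shrink with more patients: the standard error falls and the offset stays.

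At stake is the absolute gap between patients and the general population, which the protocol presents as the burden of the disease. Part of that gap could reflect who enrolled and not the illness. The direction cannot be known in advance, so burden could be overstated or understated.

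**Working it through.** The protocol states no figure for the norm comparison, so there is none to reproduce. The check is a sensitivity calculation.

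**Inputs**
- n = 194 (protocol, sections III and V.A).
- Thresholds for individual change: 6.5 points (physical summary) and 7.9 points (mental summary) (protocol, VIII.B).
- Assumed, not in the protocol: SD 10 for a summary score; difference between the sexes in the norms 1 to 3 points; difference in sex share between sample and norm population 10 to 20 percentage points.

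**Bias in the baseline gap to the norm**

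Bias = (difference in sex share) × (difference in score between the sexes)
- Low end: 0.10 × 1 = 0.1 points.
- High end: 0.20 × 3 = 0.6 points.

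The sign depends on which sex is over-represented.

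**Against sampling error**

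Standard error = 10 / √194 = 0.72 points, and the 95% half-width = 1.96 × 0.72 = 1.41 points. The bias is therefore 0.1/0.72 = 0.14 to 0.6/0.72 = 0.84 standard errors.

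A wider range of inputs, in SD units (share difference 0 to 0.30, subgroup difference 0.1 to 0.3 SD), gives at most 0.30 × 0.3 = 0.09 SD per factor. The 95% half-width is 1.96 / √194 = 0.14 SD.

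**Effect on change and on the randomised comparison**

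Let b be the offset from the sex mix.
- Gap at baseline = true gap at baseline + b.
- Gap at follow-up = true gap at follow-up + b.
- Difference between the two: b cancels, apart from any change in sex mix through dropout.
- Between arms: b is the same in expectation, because patients are randomised.
- Primary endpoint: each patient is classified by the change in his or her own scores against 6.5 and 7.9 points. No population norm adjustment enters that change.

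**Side check: the memory rule in VI.A, item 7**

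The protocol does not say how many scores count as tests of memory, so 2 to 4 were assumed. The rule (2 SD below the mean on any one test, or more than 1 SD below on two) was simulated for people with normal memory and correctly fitting norms. There were 400,000 draws, with correlation between tests from 0 to 0.6.

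| Memory tests | Share flagged |
|---|---|
| 2 | 6.3 to 8.6% |
| 3 | 11.6 to 13.8% |
| 4 | 17.6 to 18.2% |

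So about 6 to 18% of people with normal memory meet the definition. This is a property of the rule itself, and correcting the norms for sex or education would not remove it.

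**The case against.** The case against raising this is fair in most respects.

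- **Age adjustment is a coherent choice for a descriptive comparison, and the norm table could be left to an analysis plan.** This stands in part: nothing here is a contradiction. But VIII.B does not leave the adjustment open. It names age and nothing else, so the suggestion changes a stated method and does not fill a gap.
- **The effect is small.** This stands. Under the assumptions above the bias stays below one standard error and far below 6.5 and 7.9 points.
- **Repeating the comparison at follow-up adds little.** This stands. The offset cancels from change over time and is equal in expectation between arms.

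A reader might also infer three stronger points that the protocol does not support.

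- *That the protocol contradicts itself by naming sex and education as confounders and then ignoring them.* The list concerns balance between the randomised groups, not the norms. That both variables are recorded is itself an inference: section VI.A mentions only demographic data, without listing the items.
- *That the memory-impairment rate is a biased output of the trial.* Item 7 defines impairment, but nothing in the protocol says that a proportion will be reported, tested or compared with a norm, and it is not among the five objectives. The text also does not say that the published norms are corrected for age alone, and the tables are not at hand.
- *That a misfit of 0.25 to 0.5 SD could greatly inflate that rate.* No source supports such shifts. The SF-36 inputs above correspond to 0.1/10 = 0.01 to 0.6/10 = 0.06 SD. Even with a share difference of 30 percentage points, 0.5 SD would need a subgroup difference of 0.5/0.30 = 1.7 SD. A shift in the other direction would lower the rate.

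**Conclusion.** The point holds as a minor improvement to one descriptive result. Adjusting for age only leaves any difference in sex mix in the absolute gap between the patients' baseline scores and the population norm. The size is 0.1 to 0.6 points in either direction, against a standard error of about 0.72. This rests on the assumed sex difference, share difference and SD. The protocol gives none of them, so the true bias could be close to zero.

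The primary endpoint, the comparison between arms, alpha, power and sample size are untouched, and change relative to the norms is essentially so. For the memory rule only a conditional remark remains: if a proportion impaired is reported, it cannot be interpreted without knowing that the rule flags roughly 6 to 18% of people with normal memory.

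**What to change.** In VIII.B, replace the age adjustment with standardisation of the general population norms to the sample's age-by-sex distribution wherever such norms exist. Footnote any scale, for example a MOS scale, for which only age norms are available.

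Optional, in VI.A, item 7: if a memory-impairment proportion is to be reported, use education-corrected norms where published, and say which tests lack them. Give beside the observed proportion the one that the same rule would flag in people with normal memory, once the number of memory tests is fixed.

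The cost is a different norm table, one sentence of text and a footnote. No new patients, visits or tests are needed, provided that sex and education are among the demographic items recorded at entry. The drawback is that scales or tests without finer norms stay age-corrected, so the adjustment will not be uniform.

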18 chronic active infection by *B. burgdorferi* that has escaped control or eradication with the
19 use of conventional antibiotic regimens ^{10 11}. A second possibility is that CLD may be
20 due to damage caused by the original infectious process, including triggering of post-
21 infectious immune phenomena, despite the eradication of the spirochete¹². A third
22 possibility is the presence of a co-infection with another organism transmitted by Ixodes
23 ticks.

24
25 **II. OBJECTIVES**

26
27 The objectives of this study are to determine whether: 1) intensive antibiotic treatment
28 benefits seropositive patients with CLD; 2) evidence of persistent infection with *Borrelia*
29 *burgdorferi* can be found in patients with CLD; 3) evidence of co-infection with other
30 microorganisms can be found in patients with CLD; 4) specific clinical or laboratory

1 parameters improve in patients who receive antibiotic therapy compared to patients who
2 receive placebo and 5) specific parameters are predictive of a response to therapy should
3 it be observed.

4 5 **III. DESIGN AND STUDY DESCRIPTION**

6
7 This study, which is being supported as contract through funds made available by the
8 NIAID, is a Phase III, randomized, double-blinded, placebo-controlled, multicenter trial
9 (two centers). One hundred ninety four (194) patients will be enrolled in the study. Each
10 patient will be assigned to one of three strata based upon the duration of symptoms of
11 chronic Lyme disease (less than four years, four to less than eight years, or eight to less
12 than twelve years), and randomized to receive either antibiotic therapy or placebo in a 1:1
13 ratio. Antibiotics and placebo will be administered both intravenously and orally.
14 Separate randomization schedules will be generated for each study center by NIAID or its
15 designate. The study population will include a defined cohort of patients with CLD who
16 meet the inclusion and exclusion criteria as defined for this study (see section V).

17
18 The antibiotic regimen will be ceftriaxone, 2.0 grams/ day, administered once daily via
19 the intravenous route for 30 consecutive days followed by doxycycline, 200 mg/day,
20 administered as 100mg twice daily via the oral route for 60 consecutive days. Placebos
21 identical to the intravenous and oral medications will be administered via the same route
22 and for the same duration to the patients randomized to the placebo treatment group.

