4 placebo rate is 0.4 and the expected treated rate is 0.65, we need a total of 124 (62
5 patients per group) to attain 80% power at a 0.05 (two-sided) level³¹. Dividing by 0.85 to
6 allow for 15% dropouts gives a total of 146 patients. To achieve a 90% power, requires
7 194 patients with the same assumptions. The latter corresponds to an analysis with a 95%
8 confidence interval half width of approximately 0.15. The sample size of 194 is also
9 sufficient to allow us to rule out, at a one sided 0.025 level, a benefit of treatment as high
10 as 0.25 in the healing rate, if the true healing rates are 0.4 for both the antibiotic treatment
11 and placebo³².

12
13 As an interim analysis it is appropriate to consider performing the study on seropositive
14 patients with a sample size designed to show whether antibiotic treatment is equivalent to
15 placebo treatment (a trial of equivalency). To determine the sample size necessary to
16 show this, we need to define what "not effective treatment" means and to define the
17 proportion of cases that would improve naturally without treatment or would improve by
18 placebo treatment. We define treatment as ineffective if we can be reasonably sure (95%)
19 that the difference between the healing rate under treatment (pE) and the natural healing
20 rate (pS) is no greater than a defined magnitude (d). This is equivalent to showing that
21 there is a high probability that the upper bound on a confidence interval for $|pE - pS|$) is
22 less than d. (R. Makuch and R. Simon, Cancer Treatment Reports 62: 1037-1040, 1978).
23 We shall assume that the natural healing rate is 0.10 or 10%. Then in order to have a
24 minimum of 5 expected events (i.e. improvement) in the placebo group, we need a
25 sample size of 50 in the placebo group. Assuming that the rate of improvement in the
26 antibiotic treated group is the same as in the placebo treated group ($pE = pS$) and that
27 there are 50 patients in each group, there is a 99% chance that we will be able to exclude
28 any treatment difference greater than 25% using a 95% confidence interval (i.e., the
29 power is 0.99 for $d=0.25$ and $\alpha=0.05$). This sample size also gives 95% power for
30 detecting a 20% treatment efficacy ($d=0.20$) and power = 0.80 for 15% ($d=0.15$). By

1 assuming a drop-out rate of 10% from each group a sample size of 55 patients in each
2 group, or a total of 110 patients, would be required to be enrolled at the time of interim
3 analysis.

4

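### The primary chi-square test is valid and meets its stated power, but it omits the randomisation strata and baseline SF-36, and further adjustment hangs on baseline balance tests

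*Protocol*

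**What the plan says.** Section III places each patient in one of three symptom-duration bands (under 4, 4 to under 8, 8 to under 12 years) and randomises 1:1. It adds: "Separate randomization schedules will be generated for each study center by NIAID or its" designate. With two centres this gives six cells.

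Section VIII.B classifies each patient as improved or not from changes on two SF-36 summary scales, with thresholds of 6.5 points (physical) and 7.9 points (mental). The intent-to-treat primary analysis compares the "proportion of patients improved at 6 months in the placebo and treated groups" by a chi-square test at 0.05, with risk ratio, risk difference and 95% confidence intervals. No stratum or covariate is named for that test.

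On adjustment, the section says: "Tests will be done to ensure that no important potential confounders are unevenly" distributed between the groups. Regression is then to determine "the effect on results if any confounders are identified. An analysis stratified by duration" of symptoms, the text goes on, will be carried out, and so will one by site. These two stratified analyses do not depend on the balance tests, but neither is called primary. The candidate confounders are given as examples. Symptom duration is among them; baseline SF-36 is not.

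**The concern.** There are three weaknesses.

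- **Strata.** The design balances the arms on centre and duration, but the primary test does not use that balance. If either factor predicts improvement, the unstratified standard error is somewhat too large, and the test is slightly conservative.
- **Baseline score.** The endpoint is a gain from baseline beyond a fixed threshold. The chance of such a gain plausibly depends on the starting score, through regression to the mean and limited room to improve. Baseline SF-36 enters the change scores but is not a covariate.
- **Balance tests.** Under randomisation any baseline difference arises by chance, so these tests examine a null hypothesis that is known to be true. They choose covariates by imbalance, and the adjusted model is known only once the data are seen. Symptom duration shows the problem: because it is stratified it will rarely look unbalanced, so the rule would rarely select it, however prognostic it is.

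At stake are some power and precision, and an adjusted result with no fixed specification. Precision matters in both directions, because Section VIII.C also intends to rule out a benefit as high as 0.25.

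**Working it through.** **1. The plan's own figures (Section VIII.C).** The inputs are "placebo rate is 0.4 and the expected treated rate is 0.65, we need a total of 124 (62" "patients per group) to attain 80% power at a 0.05 (two-sided) level", and then "allow for 15% dropouts gives a total of 146 patients. To achieve a 90% power, requires" "194 patients with the same assumptions. The latter corresponds to an analysis with a 95" per cent confidence interval half-width of about 0.15.

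With pooled variance under the null and no continuity correction, the size per group is

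n = [1.96·√(2·0.525·0.475) + z·√(0.40·0.60 + 0.65·0.35)]² / 0.25²

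- 80% power (z = 0.842): 62 per group, 124 in total; 124/0.85 = 146.
- 90% power (z = 1.282): 82 per group, 164 in total; 164/0.85 = 193, or 194 in two equal groups.
- 194 × 0.85 ≈ 165 evaluable (82.45 per arm): power 90.2%; half-width 1.96·√(0.4675/82.45) = 0.148.

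The stated figures reproduce. The unadjusted test delivers what the protocol claims for it.

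**2. Approximate effect of adjustment.** The protocol gives no prognostic strength, so R² is an assumption. The variance is multiplied by (1 − R²), with 82.45 evaluable per arm.

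| Assumed R² | Power | Half-width | Enrolled N for 90% power |
|---|---|---|---|
| 0 | 90.2% | 0.148 | 193 |
| 0.05 | 91.6% | 0.144 | 183 |
| 0.10 | 93.0% | 0.140 | 174 |
| 0.20 | 95.4% | 0.132 | 154 |

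**3. Simulation.** Settings: 165 evaluable patients, 4,000 runs each, arms balanced within six centre-by-duration cells, rates of 40% and 65%. Assumed: duration bands of 45/35/20%, equal centres, and one baseline covariate standing in for SF-36. R² covers strata and covariate together.

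| R² | Chi-square | Cochran-Mantel-Haenszel on strata | Adjusted logistic |
|---|---|---|---|
| 0 | 88.6% | 88.9% | 89.4% |
| 0.04 (strata only) | 90.0% | 91.3% | 91.8% |
| 0.05 | 90.5% | 90.9% | 92.0% |
| 0.12 | 90.0% | 91.1% | 93.3% |
| 0.19 | 89.1% | 90.0% | 95.0% |

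Stratifying alone adds 0.3 to 1.3 points. In the three settings with a prognostic baseline covariate, the adjusted model adds 92.0 − 90.5 = 1.5, 93.3 − 90.0 = 3.3 and 95.0 − 89.1 = 5.9 points. The simulation standard error of one power figure is √(0.9·0.1/4000) = 0.005, about half a point, so the differences in the R² = 0 row should not be read as a gain.

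Simulated type I error was 4.3 to 5.3% for chi-square, 4.6 to 5.1% for Cochran-Mantel-Haenszel and 4.7 to 5.4% for logistic regression.

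**4. How conservative the crude test could be.** Assume placebo rates of 25, 40 and 55% in three equal-sized bands. The pooled variance is 0.40·0.60 = 0.24. The mean within-band variance is (0.1875 + 0.24 + 0.2475)/3 = 0.225. The ratio is 1.067, so the effective critical value is 1.96·√1.067 = 2.024 and the true level is about 4.3%.

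**The case against.** The strongest reply is that nothing here is an error. A chi-square test of two randomised proportions is valid, matches the sample-size calculation and reaches its design power. Its only possible fault is mild conservatism, which cannot produce a false claim of benefit. The two randomisation factors do get their own analyses, without condition. The regression is described as showing the effect on results, so it is a sensitivity check and nothing lets it replace the primary test. Covariate lists are also commonly left to a statistical analysis plan, which is not at hand.

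Most of this stands, and it rules out several readings that a reader might infer:

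- That the primary test is invalid or the trial underpowered. The reproduced figures show otherwise.
- That all adjustment depends on balance tests. Only the additional regression does.
- That baseline SF-36 goes unused. It forms every change score and is compared with population norms; it is only not named as a covariate.
- That baseline SF-36 is the strongest predictor available, or that the gain is assured. The protocol has no data on either.
- That the change is free. It is cheap, but it needs a rule for sparse cells and standardised estimates.

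The deferral argument does not remove the point. The protocol itself names the primary test and the trigger for adjustment, and both can be judged as written.

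**Conclusion.** This is an improvement in efficiency and prespecification, not the correction of an error. The primary test omits the factors used in randomisation and the baseline value of a change-based endpoint, and the balance-test trigger is a poor way to choose covariates.

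The size of the gain rests on assumed prognostic strength: about 0 to 1 point of power from the strata alone, and about 1.5 to 6 points with baseline SF-36 for R² of 0.05 to 0.20. The half-width would fall from 0.148 to 0.140 at R² = 0.10 or 0.132 at R² = 0.20. If the factors are not prognostic, the gain is about zero. The simulation uses a single covariate, whereas the real endpoint combines two summary scales with a condition that neither is worse, so the upper figures are indicative only.

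The criticism of the balance-test trigger needs no such assumption. Its consequence is confined to the supportive regression and leaves the primary result untouched.

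**What to change.** Amend Section VIII.B as follows:

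1. **Primary 6-month analysis.** Preferably a prespecified logistic model with treatment, centre, duration band and the baseline SF-36 physical and mental summary scores, reporting standardised risk difference and risk ratio with 95% confidence intervals. Alternatively, a Cochran-Mantel-Haenszel test stratified by centre and duration band, with stratified risk difference and risk ratio. One of the two should be named in advance.
2. **Supportive analysis.** Keep the crude chi-square test.
3. **Covariates.** Delete the balance-test trigger and give a fixed covariate list chosen for expected prognostic value. Baseline characteristics can still be tabulated by arm.

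The cost is wording only, since all the data are already collected. The downside is small. Six cells share about 165 evaluable patients, an average of 27.5 each. If the longest-duration band held 20% of patients and the centres were equal (both assumed), each of its cells would hold about 165 × 0.20 × 0.5 = 16.5. A rule for pooling adjacent duration bands should therefore be written before unblinding. The logistic estimates must be standardised, because the model itself gives a conditional odds ratio and not the planned risk difference and risk ratio. The planned sample size need not change.
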